6.7.7. Dose Decreases of Ruxolitinib for Safety

Dose modifications/interruptions of ruxolitinib because of toxicity are not required unless piasclisib modifications/interruptions have been first implemented for 14 days with no improvement in toxicity grade. Doses of ruxolitinib may be modified/interrupted earlier if the study investigator deems this necessary. Dose interruptions and modifications for ruxolitinib because of hematologic toxicity that continues after interruption of INCB050465 are shown in [Table 13](#).

Table 13: Dose Reductions/Interruptions and Restarts for Hematologic Toxicities That Persist for > 14 Days After Interruption of Parsaclisib

ANC ($\times 10^9/L$)			Platelet Count ($\times 10^9/L$)		Dose of Ruxolitinib
Value	CTCAE Grade		Value	CTCAE Grade	
0.5 to < 1.0	3	or	25 to < 40	Below UL of Grade 3	If Grade 3 cytopenia persists for > 14 days after interrupting parsaclisib/matching placebo or if the primary investigator deems that earlier interruption of ruxolitinib is necessary , then ruxolitinib will be interrupted until the toxicity is resolved to \leq Grade 1 or pretherapy baseline and then restarted at the current dose. If a Grade 3 event recurs and persists for > 14 days after interrupting parsaclisib/matching placebo or if the primary investigator deems that earlier interruption of ruxolitinib is necessary, then ruxolitinib will be interrupted and the restart dose (after recovery to \leq Grade 1 or pretherapy baseline) of ruxolitinib will be 1 dose level (5 mg BID less) lower than the dose that resulted in the cytopenia. A participant who was taking 5 mg BID will restart at 5 mg QD.
< 0.5	4	or	< 25	4	If Grade 4 thrombocytopenia or neutropenia occurs and persists for > 14 days after interrupting parsaclisib/matching placebo or if the primary investigator deems that earlier interruption of ruxolitinib is necessary , then ruxolitinib will be interrupted until toxicity is resolved to \leq Grade 1 or pretherapy baseline and the restart dose will be 1 dose level (5 mg BID less) lower than the dose that resulted in the cytopenia. A participant who was taking 5 mg BID ruxolitinib will restart at 5 mg QD.
Neutropenic fever					If neutropenia (ANC < 1.0) persists for > 14 days after interrupting parsaclisib/matching placebo or if the primary investigator deems that earlier interruption of ruxolitinib is necessary, then ruxolitinib will be interrupted until recovery of ANC to $\geq 1.0 \times 10^9/L$ and the restart dose will be 1 dose level (5 mg BID less) lower than the dose that resulted in the cytopenia.

6.8. Concomitant Medications and Procedures

All concomitant medications and treatments (including over-the-counter or prescription medicines, vitamins, vaccines, and/or herbal supplements) must be recorded in the eCRF. Any prior medication received up to 30 days before the first dose of study treatment and 30 to 35 days after the last dose of study treatment, or until the participant begins a new MF therapy, whichever occurs first, will be recorded in the eCRF. Any addition, deletion, or change in the dose of these medications will also be recorded. Concomitant medications administered after the last dose of study treatment should be recorded for SAEs as defined in Section 9.2. Prior medication history for MF should be entered in its entirety, as well as complete ruxolitinib dosing history.

6.8.1. Permitted Medications

Concomitant treatments/procedures that are required to manage a participant's medical condition during the study will also be recorded in the eCRF. The medical monitor should be contacted if there are any questions regarding concomitant or prior therapy for conditions other than MF.

6.8.2. *Pneumocystis jirovecii* Pneumonia Prophylaxis

All participants receiving combination study treatment with pascalisib/matching placebo and ruxolitinib are required to receive a standard PJP prophylaxis regimen determined by the investigator. Examples of standard PJP prophylaxis therapies for this population include trimethoprim-sulfamethoxazole, atovaquone, diaminodiphenylsulfone (Dapsone) with or without pyrimethamine, and pentamidine ([National Comprehensive Cancer Network 2017](#)). *Note:* In Japan, diaminodiphenylsulfone and pentamidine are not approved for PJP prophylaxis, thus these will not be used. Participants with sulfonamide allergy should be treated with either inhaled pentamidine or atovaquone for PJP prophylaxis; diaminodiphenylsulfone should not be used in such participants. Prophylaxis should be given while participants are receiving pascalisib and continue for 2 to 6 months after the last dose of study treatment. Prophylaxis may be started as soon as the baseline visit but no later than Day 1 of the study.

6.8.3. Use of Growth Factors such as Erythropoietin

Hematopoietic growth factor receptor agonists (eg, erythropoietin, granulocyte-colony stimulating factor, romiplostim, eltrombopag) are strongly discouraged. Ruxolitinib may interfere with efficacy of growth factors, and they may cause an increase in spleen size.

6.8.4. Restricted Medications and Procedures

- Aspirin in doses exceeding 125 mg/day is not permitted. Low-dose aspirin (≤ 125 mg/day) is permitted.
- Caution should be used when administering ibuprofen or other nonsteroidal anti-inflammatory drugs. Systemic corticosteroid doses less than or equal to the equivalent of 10 mg prednisolone per day are permitted, and higher dosages are not allowed. Participants should be monitored closely for toxicity, especially for myelosuppression and renal and gastrointestinal toxicity.
- Inducers of CYP3A4 may be used with caution, and investigators should seek other options if available (see [Appendix G](#)).
- Moderate CYP3A4 inhibitors may be used with caution. Differences in individual sensitivity and variation in potency of inhibition of various CYP enzymes may result in the need for a reduced dose of ruxolitinib during a period of concomitant medication use. If required for safety, the dose of ruxolitinib may be reduced from BID to QD in these circumstances; this should be clearly documented in the treating physician's notes. The sponsor's medical monitor may be consulted for advice when using these agents.

If concomitant administration of an anticoagulant/antiplatelet medication is indicated, then caution and enhanced monitoring is required. History of thrombocytopenia and any concurrent ruxolitinib-related thrombocytopenia should be a factor in the choice of anticoagulant and dose.

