6.7.2. Dose Decreases of Parsaclisib/Placebo for Toxicity

Parsaclisib or matching placebo should be interrupted/decreased first, with no change to the ruxolitinib dosage. Adjustments to ruxolitinib may be utilized if interruption/dose adjustment of parsaclisib or matching placebo does not lead to resolution or at least improvement of the AE within a 14-day period (see Section 6.7.7). Treatment with parsaclisib or matching placebo may be delayed up to 2 weeks (14 days) to allow for resolution of toxicity. Participants may resume

treatment if no medical condition or other circumstance exists that, in the opinion of the investigator, would make the participant unsuitable for further participation in the study. The treating investigator should contact the sponsor to discuss the case of any participant whose treatment has been delayed for more than 14 days before restarting treatment with piasclisib or matching placebo and/or ruxolitinib. Adverse events that have a clear alternative explanation or transient (≤ 72 hours) abnormal laboratory values without associated clinically significant signs or symptoms may be exempt from dose-reduction rules.

Table 11 shows dose-reduction and interruption guidelines for piasclisib and matching placebo. Because participants may enter the study with extensive pretreatment and/or severe bone marrow infiltration by the primary disease, these dose-reduction rules are provided as guidelines (see **Table 11**). **Individual decisions regarding dose reduction/interruption should be made using investigator clinical judgment and in consultation with the sponsor's medical monitor in those cases where the guidelines will not be followed, taking into account relatedness of the AE to piasclisib and the participant's underlying condition.** Available dose strengths for piasclisib/matching placebo are shown in **Table 12**.

Table 11: Guidelines for Interruption and Restarting of Piasclisib/Matching Placebo

Adverse Event	Action Taken
Chemistry	

 • AST and/or ALT $> 5.0 \times$ ULN (Grade 3). 	
Step 1: Interrupt piasclisib or matching placebo for up to 2 weeks (14 days) until the toxicity has resolved to \leq Grade 1 except by approval of the medical monitor.
 
Step 2: Restart piasclisib or matching placebo at the same dose. If assessed as related to piasclisib or matching placebo, restart piasclisib or matching placebo at the next lower dose; monitor as clinically indicated.

Hematology	

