
 • ANC $< 1.0 \times 10^9/L$ (Grade 3) unless because of underlying disease. Applies only if this represents a worsening grade from baseline. • Platelet count $\geq 25 \times 10^9/L$ and $< 40 \times 10^9/L$. Applies only if this represents a worsening grade from baseline. 	
Step 1: Interrupt piasclisib or matching placebo for up to 2 weeks (14 days) until the toxicity has resolved to \leq Grade 1 or pretherapy baseline.
 
Step 2: Restart piasclisib or matching placebo at the same dose and monitor as clinically indicated.

 • Grade 4 ANC ($< 0.5 \times 10^9/L$) regardless of baseline grade. • \geq Grade 3 ANC with temperature of at least $38.5^\circ C$ OR with \geq Grade 3 infection regardless of baseline grade. • Platelet count is $< 25 \times 10^9/L$ (Grade 4), regardless of baseline grade. 	
Step 1: Interrupt piasclisib or matching placebo for up to 2 weeks (14 days) until the toxicity has resolved to \leq Grade 1 or pretherapy baseline.
 
Step 2: Restart piasclisib or matching placebo at the next lower dose; monitor as clinically indicated. Escalate to original dose with recovery to preinterruption levels of analyte.

Nonhematologic toxicities	

 • Diarrhea/colitis (Grade 1) 	
Step 1: Treat with antimotility agents (eg, loperamide) and initiate supportive care. If not improved after 48 hours, treat per guidance for Grade ≥ 2.

Table 11: Guidelines for Interruption and Restarting of Parsaclisib/Matching Placebo (Continued)

Adverse Event	Action Taken

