
 • Diarrhea/colitis (Grade 2) 	
Step 1: Interrupt parsaclisib or matching placebo. Perform workup for infection (including CMV, Clostridium difficile, etc) immediately. Initiate or continue supportive care. Monitor approximately every 48 hours until resolution.
 
Step 2: If improved within 48 hours and/or infection* is confirmed, restart parsaclisib/matching placebo at the same schedule and dose after resolved to \leq Grade 1 and continue to monitor.
 
*For infectious diarrhea/colitis, follow institutional standard of care guidelines and restart parsaclisib/matching placebo according to clinical judgment after resolved to \leq Grade 1. Consult with medical monitor if needed.
 
Step 3: If not improved within 48 hours and infection is ruled out, start oral steroids or consider IV steroids if participant is being given IV fluids. If no improvement with oral steroids, switch to IV steroids.
 
Step 4: When diarrhea resolves to \leq Grade 1, continue supportive care and taper steroids according to institutional standard of care. When taper is complete (eg, no steroid or \leq 10 mg/day prednisone or equivalent) and diarrhea is \leq Grade 1, restart parsaclisib/matching placebo at the next lower dose with approval of the medical monitor.
 
Step 5: If Grade 2 diarrhea reoccurs, treat per guidance for diarrhea (\geq Grade 3)/noninfectious colitis.
 
Step 6: If \geq Grade 2 diarrhea reoccurs a third time, permanently discontinue parsaclisib/matching placebo.

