
 • Diarrhea (\geq Grade 3) Noninfectious colitis (any grade; confirmed or suspected) 	
Step 1: Interrupt parsaclisib. Perform workup for infection (including CMV, C difficile, etc) immediately. Initiate or continue supportive care (see Section 6.7.3). Consider colonoscopy with biopsy for diarrhea \geq Grade 3 and/or if symptoms suggestive of colitis (diarrhea accompanied by abdominal pain and/or mucus or blood in stool). Monitor every 48 hours until resolution.
 
Step 2: If infection* is ruled out, start oral steroids or consider IV steroids if participant is being given IV fluids. If no improvement with oral steroids within 48 hours, switch to IV steroids.
 
*For infectious diarrhea/colitis, follow institutional standard of care guidelines and restart parsaclisib according to clinical judgment after resolved to \leq Grade 1. Consult with medical monitor if needed.
 
Step 3: When diarrhea/colitis resolves to \leq Grade 1, continue supportive care and taper steroids according to institutional standard of care. When taper is complete (eg, no steroid or \leq 10 mg/day prednisone or equivalent) and diarrhea/colitis is \leq Grade 1, restart parsaclisib with approval of the medical monitor. Continue to monitor.
 
Step 4: If \geq Grade 3 diarrhea or noninfectious colitis (any grade) reoccurs, permanently discontinue parsaclisib/placebo.

Table 11: Guidelines for Interruption and Restarting of Parsaclisib/Matching Placebo (Continued)

Adverse Event	Action Taken

 • Pneumonitis (Grade 1) 	
Step 1: Interrupt parsaclisib or matching placebo until the toxicity has resolved.
 
Step 2: Restart parsaclisib or matching placebo at the next lower dose. Monitor as clinically indicated.

 • Pneumonitis (\geq Grade 2) 	
Permanently discontinue parsaclisib or matching placebo.

 • Skin toxicity (eg, rash, pruritus, etc, unless otherwise specified) (Grade 2-3) 	
Step 1: Interrupt parsaclisib or matching placebo until the toxicity has resolved to \leq Grade 1.
 
Step 2: Restart parsaclisib or matching placebo at the same dose. If assessed as related to parsaclisib or matching placebo, restart at the next lower dose.

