6.7.3. Supportive Care for Diarrhea/Colitis

Participants should be informed to immediately report to the investigator any event of diarrhea. Participants should receive appropriate supportive care measures as deemed necessary by the investigator. For any \geq Grade 1 diarrhea, participants should be advised to drink liberal quantities of clear fluids. If sufficient oral fluid intake is not feasible, fluid and electrolytes should be substituted via IV infusion. Participants should try to eat 5 to 6 small meals per day; low-fat, high-protein foods; and cooked instead of raw vegetables. Participants may supplement their diet with bananas, rice, applesauce, and toast to reduce the number of bowel movements and may also try crackers, gelatin, noodles, or oatmeal. Participants should avoid fried, fatty, greasy, or spicy foods; milk, milk products, and acidic drinks; high-fiber foods and foods that cause gas; and alcohol, caffeine, and herbal supplements (Coutré et al 2015).

For each occurrence, attempts should be made to rule out other causes, such as metastatic disease or bacterial or viral infection (including CMV), which might require additional supportive care.

It may be necessary to perform conditional procedures such as colonoscopy with biopsy as part of evaluation of the event. Note that several courses of steroid tapering may be necessary because symptoms may worsen when the steroid dose is decreased.

Participants should be carefully monitored for signs and symptoms of enterocolitis (such as diarrhea, abdominal pain or cramping, and blood or mucus in stool, with or without fever) and of bowel perforation (such as peritoneal signs and ileus).

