Description of change: Specified that individual decisions are in regard to both dose reductions and interruptions.

Rationale for change: To provide additional clarity to dosing decisions.

26. Section 6.7.2, Dose Decreases of Parsaclisib/Placebo for Toxicity (Table 11: Guidelines for Interruption and Restarting of Parsaclisib/Matching Placebo)

Description of change: Removed the requirement for temperature to be measured orally in the event of a Grade 3 or higher ANC and fever, added a description of symptoms of colitis, and added another step for treatment of Grade 3 or higher diarrhea or noninfectious colitis.

Rationale for change: To allow body temperature to be measured by any modality for neutropenic fever and administrative errors.

27. Section 6.7.5, Criteria for Permanent Discontinuation of Parsaclisib/Matching Placebo

Description of change: Removed wording regarding exceptions by sponsor for study drug discontinuation because of AEs requiring more than 2 dose reductions.

Rationale for change: UK MHRA request.

28. Section 6.7.6, Dose Decreases of Ruxolitinib for Safety

Description of change: Clarified that, at the investigator's discretion, ruxolitinib dose interruptions/changes for safety reasons may occur before the end of a 14-day period after the parsaclisib dose was modified or interrupted for safety reasons.

Rationale for change: UK MHRA request.

29. Section 6.8.2, *Pneumocystis jirovecii* Pneumonia Prophylaxis

Description of change: Specified that diaminodiphenylsulfone and pentamidine will not be used for PJP prophylaxis in Japan.

Rationale for change: Japan requirement.

30. Section 6.8.3, Use of Growth Factors Such as Erythropoietin

Description of change: Added section advising caution on concomitant use of growth factors.

Rationale for change: To address multiple questions regarding allowance of growth factors from investigative sites.

31. Section 6.8.4, Restricted Medications and Procedures

Description of change: Modified text regarding use of nonsteroidal anti-inflammatory drugs and added text restricting the dosage of corticosteroids.

Rationale for change: To recommend caution when administering nonsteroidal anti-inflammatory drugs in general and to provide guidance for steroid therapy, which may be used as supportive care, as use of these corticosteroids at high doses may interfere with readout of study endpoints.

32. Section 8, Study Assessments and Procedures

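### Protocol 6.8.4 bars systemic steroids above 10 mg prednisolone-equivalent per day without exception, while Table 11 directs oral or IV steroids for diarrhea/colitis with a taper down to that level

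*Protocol*

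**What the plan says.** Section 6.8.4 of the protocol (Restricted Medications and Procedures) reads: "Systemic corticosteroid doses less than or equal to the equivalent of 10 mg prednisolone per day are permitted, and higher dosages are not allowed". It gives no exception for managing toxicity and does not refer to Table 11.

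Table 11 in Section 6.7.2 handles diarrhea and colitis in three entries:

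- **Grade 1 diarrhea/colitis:** antimotility and supportive care first, then "If not improved after 48 hours, treat per guidance for Grade" 2 or higher.
- **Grade 2 diarrhea/colitis:** interrupt parsaclisib or placebo. If there is no improvement within 48 hours and infection is excluded, start steroids by mouth or consider the IV route. Restart follows a completed taper, described by way of example as no steroid or at most "10 mg/day prednisone or equivalent) and diarrhea is" Grade 1 or lower.
- **Grade 3 or higher diarrhea, or non-infectious colitis of any grade:** steroids once infection is excluded, with the instruction "If no improvement with oral steroids within 48 hours, switch to IV steroids". The restart condition is the same: no steroid or at most "10 mg/day prednisone or equivalent) and diarrhea/colitis is" Grade 1 or lower.

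Section 6.7.3 adds: "Note that several courses of steroid tapering may be necessary because symptoms may worsen when the steroid dose is decreased". Section 6.7.4 sends the reader to Table 11 for the care of immune-related events. Neither section mentions the cap in 6.8.4.

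On the status of Table 11, Section 6.7.2 says "these dose-reduction rules are provided as guidelines". In Appendix J (Amendment 1, item 31) the stated reason for adding the cap is partly "to provide guidance for steroid therapy, which may be used as supportive care", together with a concern that high doses may interfere with endpoint readout.

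**The concern.** A site treating non-infectious diarrhea or colitis by Table 11 would be expected to exceed the dose limit in 6.8.4. A site holding to 6.8.4 literally could not use the Table 11 taper as it is evidently meant. Investigators should not have to choose between two parts of the protocol while managing an event that the protocol itself singles out: colitis, and diarrhea of Grade 2 or higher, are adverse events of special interest in Section 9.5. Section 2.6.1.3 also reports fatal or serious diarrhea or colitis with other PI3K inhibitors (14%-20% for idelalisib, 18% for duvelisib). Those are other drugs in other diseases, so they show why the instruction must be clear but do not size the problem here.

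There is a smaller analysis consequence. SAP 5.3.2 identifies per-protocol exclusions partly from protocol deviations and from concomitant medications under Protocol Section 6.8. Participants managed as Table 11 directs could therefore be flagged as deviating, possibly more often in one arm than the other.

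**Working it through.** No sample size, power, alpha or event count enters this point, so there is nothing to recompute. The check sets the passages against each other.

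**1. The shared figure.**

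| Place | Role of 10 mg/day |
|---|---|
| Protocol 6.8.4 | Highest systemic dose permitted |
| Table 11, Grade 2 diarrhea/colitis | One way for the taper to count as complete before restart |
| Table 11, Grade 3 or higher diarrhea, or non-infectious colitis | Same |

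**2. What follows if the cap always applies.** Let d be the daily systemic dose in prednisolone equivalents.

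- Section 6.8.4 requires d ≤ 10 mg on every day.
- The dose part of the Table 11 restart condition is met when d = 0 or d ≤ 10 mg.
- Under the cap, that dose part is met from the first steroid day, before any taper. Restart would then depend only on event grade and medical monitor approval, and the taper requirement would do nothing.

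The taper step therefore makes sense only if d can exceed 10 mg, which 6.8.4 does not allow. The planned switch to IV treatment and the repeated taper courses in 6.7.3 fit that reading, although neither states a dose.

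**3. How far the pathway reaches.** Two Table 11 entries contain both the steroid step and the restart threshold. Unimproved Grade 1 events escalate into them, and a recurrence at Grade 2 is sent to the Grade 3 or higher guidance.

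**4. Search for an exception.**

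- Section 6.8.4 has none.
- Section 6.8.1 provides for eCRF recording and for questions to the medical monitor; it does not lift the cap.
- Sections 6.7.2, 6.7.3 and 6.7.4 do not mention the cap.
- Section 6.8.5 does write a qualification where one was wanted: ketoconazole may be used cautiously when there is no alternative. The steroid sentence has nothing comparable.

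**5. Does interrupting study drug take the participant outside the cap?** Section 6.8.4 is not limited to days on parsaclisib or placebo. By default Section 6.7.2 leaves ruxolitinib unchanged during the interruption, so the participant is still on study treatment while receiving steroids.

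**6. Is the cap meant only for other uses of steroids?** The Appendix J rationale names supportive-care use, so the text does not support that reading.

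**7. Reach into the analyses.** The primary and key secondary analyses use the intent-to-treat population, and the stated power (83.67% for spleen response, 80.02% for symptom response, at 440 participants) does not depend on this. Protocol Table 17 lists per-protocol analyses only as supportive, for spleen response, symptom response and overall survival.

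**The case against.** The best case against is that the contradiction is inferred. Table 11 states no dose, no sentence directs more than 10 mg/day, the threshold is given only as an example with no steroid as an alternative, and moving from oral to IV is a change of route. The two passages can also be read together: Table 11 interrupts parsaclisib or placebo before steroids begin and allows restart only once the dose is nil or within the 6.8.4 limit. The specific toxicity guidance would then sit alongside a general medication rule. Amendment 1 revised both places, which may mean the sponsor saw them as compatible. Sites can consult the medical monitor, whose approval is needed for restart after a taper, and per-protocol exclusions are a clinical judgement signed before unblinding.

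Part of this stands. The conflict does rest on implication, Table 11 is guidance, consultation routes exist, and the statistical effect is minor. The combined reading fails, however, because the cap is not tied to days on parsaclisib or placebo, ruxolitinib continues by default, and nothing says Table 11 overrides 6.8.4. Guidance subordinate to a flat prohibition gives way to it, which makes the difficulty worse. The shared amendment date settles nothing either way. Consulting the medical monitor is not an exception to the cap.

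**Conclusion.** The concern holds, and the text should be fixed. As written, following 6.8.4 literally would obstruct toxicity management that the protocol directs for an event of special interest, so this is an inconsistency and not merely a missing detail. It rests on one inference, that a taper ending at 10 mg/day or less starts above 10 mg/day, and on no exception having been found in the visible text.

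In extent, one cap conflicts with two Table 11 entries, with a third feeding into them and repeat tapers foreseen. The number of participants affected and any imbalance between arms cannot be estimated from the documents. The confirmatory analyses are not at risk. The per-protocol issue is incidental, and the conclusion does not depend on it.

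**What to change.** The sponsor should reconcile Section 6.8.4 with the Table 11 diarrhea/colitis entries (Grades 1, 2, and 3 or higher) and with Section 6.7.3, so that sites have one consistent instruction on systemic steroids for these events, with cross-references between the sections. Which clinical rule is right is for the sponsor to decide.

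Once that is settled, SAP 5.3.2 should state, before unblinding, how steroid use under the reconciled text is handled in the per-protocol review, whichever way the sponsor decides.

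The cost is a short protocol amendment or clarification letter and one line in the SAP. Sample size, endpoints and the primary analysis do not change.
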